#### **6.8.4 Lost to Follow-up**

CONFIDENTIAL

This material is the property of the NYU School of Medicine. Do not disclose or use except as authorized in writing by the study sponsor

All reasonable efforts must be made to locate subjects to determine and report their ongoing status. This includes the subject's next-of-kin if the subject does not respond. Lost to follow-up is defined by the inability to reach the subject and then after a minimum of two documented phone calls, faxes, or emails in a 3 month period over two consecutive 3 month periods, a lack of response by subject to one registered mail letter, and if no medical records are available to be reviewed.

All attempts should be documented in the subject's medical records. If it is determined that the subject has died, the site will use permissible local methods to obtain the date and cause of death. The site staff will consult publicly available sources, such as public health registries and databases, in order to obtain updated contact information. If after all attempts, the subject remains lost to follow-up, then the last known alive date as determined by the investigator should be reported and documented in the subject's medical records.

## **6.9 Permanent Discontinuation of Study Treatment**

Subjects MUST discontinue investigational product (and non-investigational study treatment at the discretion of the investigator) for any of the following reasons:

- Subject's request to stop study treatment
- Any clinical adverse event (AE), laboratory abnormality or intercurrent illness which, in the opinion of the investigator, indicates that continued participation in the study is not in the best interest of the subject
- Termination of the study by the Sponsor or Bristol-Myers Squibb (BMS)
- The subject becomes pregnant. If subject becomes pregnant, the investigator must immediately (within 24 hours of awareness of the pregnancy) notify the Sponsor or designee of this event.

All subjects who discontinue study drug should comply with protocol specified follow-up procedures as outlined in Section 6.10. The only exception to this requirement is when a subject withdraws consent for all study procedures including post-treatment study follow-up or loses the ability to consent freely (i.e., is imprisoned or involuntarily incarcerated for the treatment of either a psychiatric or physical illness).

If study drug is discontinued prior to the subject's completion of the study, the reason for the discontinuation must be documented in the subject's medical records and entered on the appropriate case report form (CRF) page.

## **6.10 Withdrawal of Subjects**

### **6.10.1 When and How to Withdraw Subjects**

A subject has the right to voluntarily discontinue study treatment or withdraw from the study at any time, for any reason, and without repercussion. The investigator and sponsor have the right to discontinue a patient from study treatment or withdraw a patient from the study at any time.

Reasons for subject withdrawal from the study may include, but are not limited to:

- Subject withdrawal of consent at any time
- Disease progression
- Intolerable toxicity
- Any medical condition that the investigator or sponsor determines may jeopardize the patient's safety if he or she continues in the study or continues treatment with study drug.
- The investigator or sponsor determines it is in the best interest of the patient

CONFIDENTIAL

This material is the property of the NYU School of Medicine. Do not disclose or use except as authorized in writing by the study sponsor

- Failure of subject to adhere to protocol requirements (e.g., not complying with protocol required visits, assessments, and dosing instructions)
- Pregnancy
- Meeting of another study withdrawal or discontinuation criterion
- Death
- Study termination by Sponsor

Subjects who request to discontinue study drug will remain in the study and must continue to be followed for protocol specified follow-up procedures. The only exception to this is when a subject specifically withdraws consent for any further contact with him/her or persons previously authorized by subject to provide this information. Subjects should notify the investigator of the decision to withdraw consent from future follow-up in writing, if possible. The withdrawal of consent should be explained in detail in the medical records by the investigator, as to whether the withdrawal is from further treatment with study drug only or also from study procedures and/or post treatment study follow-up, and entered on the appropriate CRF page. The date the participant was removed, must be documented. In the event that vital status (whether the subject is alive or dead) is being measured, publicly available information should be used to determine vital status only as appropriately directed in accordance with local law.

## 6.11 Research Specimen Procedures

- See Appendix 6 for Background and Rationale of Research Correlative Studies.
- Refer to the study procedures above for details on timing of research specimen collections.

**Note:** This study involves collection of **required archival tumor tissue and blood specimens for research** as well as collection of a small amount **fresh surgical specimen** (equivalent to amount required for a stereotactic needle biopsy), if available, for short-term organotypic tumor spheroid culture and flow-cytometry-based immunoprofiling, and an **optional on-study or post-study tumor specimen** if a biopsy is required during or after protocol therapy.

All patients will be given the option to have **leftover research specimens banked for future research** after study completion and completion of protocol-defined research studies at the time of informed consent. See Section 9.1.1 for details on confidentiality and banking of leftover research samples.

### 6.11.1 Required Archival Tumor Specimen for Research

Archival tumor tissue from a previous surgical resection that demonstrates histopathological evidence of glioblastoma (GBM, WHO grade IV) or gliosarcoma as specified in the Eligibility Criteria must be submitted.

A paraffin-embedded or frozen tumor-tissue block with a minimum of 1 cm^2 surface area of viable tumor is required. The tumor block should contain at least 20% viable tumor, i.e., a representative H&E slide should show that at least 20% of the specimen contains viable tumor.

If a tumor block cannot be submitted, then twenty (20) unstained 5-micron slides (preferably 10 slides from two different tumor blocks from the same surgery) from the tumor specimen must be submitted.

Send archival tumor specimens for research to:

[name]  
Department of Pathology, NYU School of Medicine  
[name]  
[name]  
[name]

CONFIDENTIAL

This material is the property of the NYU School of Medicine. Do not disclose or use except as authorized in writing by the study sponsor

[contact]  
[contact]  
[contact]  
Email: [contact]

### 6.11.2 Required Research Blood Samples

Research blood samples will be taken at only 2 time points:

**Main Study Cohort: Pre-dose C1D1** (up to 3 days prior to C1D1) and at the **C2D1 visit (end of week 6)**.

**Surgical Study Cohort: Pre-dose C1D-29** (up to 3 days prior to C1D-29) and at the **C1D15 visit (end of week 6)**.

All subjects will have the below research blood samples collected. For details on the timing of specimen collection, refer to the study procedures.

Whole blood for research will be collected from all subjects as described below:

- **NYUSoM subjects:** A total of 40 mL (four 10 mL purple top EDTA tubes) of whole blood will be drawn and immediately sent to the below sites:
  - One (1) 10 mL tube will be sent to the CBRD at NYUSoM for acquisition of whole blood, buffy coat, and plasma samples.
  - Three (3) 10 mL tubes will be sent to the IMC at NYUSoM and immediately processed for isolation of PBMCs.

### 6.11.3 Fresh Surgical Tumor Specimen (if available)

After informed consent, if subjects undergo tumor resections or biopsies prior to treatment initiation, during the study period, or after progression on study drug, a small amount fresh surgical specimen (less than 0.5 cm^2, approximately equivalent to amount required for a stereotactic needle biopsy) will be collected for short-term (6-8 days) organotypic tumor spheroid culture and for dissociation into single cell suspensions for flow-cytometry-based immunoprofiling. Fresh tumor specimen will only be collected after verifying that enough tumor sample for diagnosis and clinical care is available. All tumor material collected will be used for these specific purposes only. Tumor sample will be collected in medium (DMEM) in a sterile cryotube and immediately transported on ice to [name] laboratory at NYU Langone for immediate processing.

### 6.11.4 Optional Tumor Biopsy for Research

If subjects undergo tumor resections or biopsies during the study period after treatment initiation, or after progression on study drug, a tumor specimen will be collected for research purposes if the subject provides consent at the time of informed consent.

A section of frozen tumor or a FFPE block (surface area of 1 cm^2 containing at least 20% viable tumor, as described above in Section 6.8.2) from the tumor surgery is preferred. If a frozen tumor specimen or a tumor block cannot be provided, then 20 unstained 5-micron slides (preferably 10 slides from two different tumor blocks from the same surgery) from the tumor block should be sent.

Send optional on-study or post-treatment tumor samples to:

[name]  
Department of Pathology, NYU School of Medicine  
[name]  
[name]

CONFIDENTIAL

This material is the property of the NYU School of Medicine. Do not disclose or use except as authorized in writing by the study sponsor

[name]  
[contact]  
[contact]  
[contact]  
[contact]

## 7 Statistical Plan

### 7.1 Background for Statistical Plan

*MGMT* unmethylated, elderly and poor functional status newly diagnosed GBM patients treated on recent randomized clinical trials with regimens including radiotherapy, temozolamide or bevacizumab have median survivals in the range of 6-12 months, with one study that did not enroll patients with unresectable (biopsy-only) tumors which carry poorer prognosis reporting 14 months. With standard chemoradiation, the fraction of patients alive at 1 and 2 years for *MGMT* unmethylated patients aged 70 or less with good functional status are 50% and 6%. The 1 year OS proportion for elderly and poor prognosis patients ranges from 21-32%.

With regards to hypofractionated radiotherapy in newly diagnosed GBM, the IAEA randomized trial treated elderly and poor functional status GBM patients aged  $\geq 50$  with hypofractionated RT (5 fraction) and the median OS was 8 months. In recent years, other small phase I and II studies have reported short course RT to have similar efficacy similar to standard treatment regimens in selected newly diagnosed GBM patients, although these studies did not stratify by *MGMT* methylation status. Median OS in these *MGMT* non-stratified studies ranged from 15 to 20 months.

Based on these historical measures, a 12 month (1yr-OS) of 35% will be considered non-promising in *MGMT* unmethylated, newly diagnosed GBM subjects; an increase in the 1yr-OS to 60% will be considered promising.

Most recently, a phase II randomized multicenter clinical study in patients with recurrent glioblastoma suggest that treatment with the PD-1 inhibitor pembrolizumab results in significantly prolonged overall survival when given neoadjuvantly (prior to tumor re-resection) as compared to pembrolizumab adjuvantly (after tumor re-resection). This increase in overall survival was associated with upregulated T cell-activation and Interferon- $\gamma$ -gene expression signatures and downregulation of cell-cycle related gene expression signatures in tumor cells. In this study, interferon- and T cell-pathway induction was seen in 9 of 14 tumors (64%) from patients who received neoadjuvant pembrolizumab compared to 5 of 15 tumors (33%) from patients who received pembrolizumab adjuvant-only.

Based on these measures, a T-cell pathway induction rate of 33% will be considered non-promising; an increase in the T-cell pathway induction rate to 64% will be considered promising.

### 7.2 Statistical Methods and Sample Size Determination

#### 7.2.1 Safety

The Safety Lead-In portion of the study will include the first 6 subjects enrolled on the Main Study Cohort. The exact number of patients enrolled in the entire study will depend on the number of protocol-defined DLTs observed and the possibility of opening additional cohorts at modified nivolumab and/or ipilimumab prescriptions as described in Section 6.1.1 (Safety Lead-In). Data for the Safety Lead-In will be summarized using descriptive statistics.

Adverse events will be graded using CTCAE version 4.03. Safety summaries will be reported for both the Safety Lead-In and the phase II trial. All subjects who received at least one dose of study drug and/or radiation will be used for the analysis of safety data in this study. Safety and tolerability will be assessed

CONFIDENTIAL

This material is the property of the NYU School of Medicine. Do not disclose or use except as authorized in writing by the study sponsor

by clinical review of all relevant parameters including adverse experiences (AEs), laboratory tests, and vital signs.

Additionally, specific immune-related adverse experiences (irAEs, as defined Section 6.2.1) will be collected and summarized in separate tables from other AEs by toxicity grade and will include the counts, percentage, and 95% CI.

Adverse events (specific terms as well as system organ class terms) and predefined limits of change in laboratory, and vital sign parameters will be summarized with descriptive statistics (counts, percentage, mean, standard deviation, etc.). Continuous measures such as changes from baseline in laboratory, and vital signs parameters will be summarized using descriptive statistics (mean, standard deviation, etc.) for baseline, on-treatment, and change from baseline values.

For toxicity monitoring statistical methods, see the Primary Safety Endpoints in Section 3.5.

### 7.2.2 Main Study Cohort - Phase II trial design

A single-stage design will be utilized to estimate overall survival, with a hypothesized 1yr-OS of 60%= $H_1$  and 35%= $H_0$ . We will enroll 24 patients; this design has a two-sided Type I error of 0.05 and a power of 80%.

For endpoint analyses, one year will be defined as 48 weeks (8 cycles) and two years will be defined as 96 weeks (16 cycles). Patients will be evaluated for radiographic responses by conventional contrast enhanced MRI every 8 weeks. Radiographic response assessments will be determined using RANO criteria for GBM.

1yr-OS and radiographic response rates will be estimated with exact 95% confidence intervals; with 24 patients, a 95% CI will be no more than 0.4 units wide. OS will be determined from the time of treatment initiation until the time of death due to any cause, with OS being censored at last follow-up if the patient remained alive. Patients who were last known to be alive and progression-free will be censored at the latest disease assessment. The Kaplan–Meier curves will be used to summarize OS and to estimate the medians.

PFS is defined as the time between treatment initiation and first occurrence of disease progression or death, and will be censored at last follow-up if the patient remained alive without disease progression. PFS is defined as the time from the first dose of study treatment to the earlier of disease progression or death due to any cause. Patients who initiate alternate anticancer therapy in the absence of documented progression will be censored at the latest disease assessment prior to initiation of such therapy. Patients with no post-baseline disease assessments will be censored at the Cycle 1 Dose 1 date unless death occurred prior to the first planned assessment (in which case the death will be considered a PFS event). The Kaplan–Meier curves will be used to summarize PFS and to estimate the medians.

Overall response rate (ORR) is defined as the proportion of patients who achieve best overall response of complete or partial response at any time after initiation of study treatment (prior to initiation of alternate anticancer treatment). Duration of response is defined as the number of months from the time criteria are first met for either CR or PR, until the first date that PD is objectively documented. The duration of objective response will be summarized descriptively using the Kaplan-Meier method.

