### *Sample Size:*

**Main Study Cohort:** Based on historical measures, a 12 month (1yr-OS) of 35% will be considered non-promising; an increase in the 1yr-OS to 60% will be considered promising. We will use a single-stage design and enroll 24 patients. This will provide 80% power to detect an increase in the 1-year OS from 35% to 60%, using a 0.05-level test.

**Surgical Study Cohort:** Based on historical measures, a T-cell pathway induction rate of 33% will be considered non-promising; an increase in the T-cell pathway induction rate to 64% will be considered promising. We will use a single-stage design and enroll 16 patients. This will provide 80% power to detect an increase in the 1-year OS from 33% to 64%, using a 0.05-level test.

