### *Endpoints:*

1yr-OS and radiographic response rates will be estimated with exact 95% confidence intervals; with 24 patients, a 95% CI will be no more than 0.4 units wide for the main study cohort. PFS, defined as the time between treatment initiation and first occurrence of disease progression or death, will be censored at last follow-up if the patient remained alive without disease progression. OS will be determined from the time of treatment initiation until the time of death, with OS being censored at last follow-up if the patient remained alive. The Kaplan-Meier curves will be used to summarize PFS and OS and to estimate the medians.

Adverse events will be graded using CTCAE version 4.03. All subjects who initiate therapy (receive at least one dose of ipilimumab and nivolumab and/or radiotherapy) will be evaluated for safety. A Bayesian monitoring approach will be applied to assess safety throughout the Phase II trial with pre-defined stopping rules.

CONFIDENTIAL

This material is the property of the NYU School of Medicine. Do not disclose or use except as authorized in writing by the study sponsor

CONFIDENTIAL

This material is the property of the NYU School of Medicine. Do not disclose or use except as authorized in writing by the study sponsor

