### 7.2.3 Phase II trial – Surgical Study Cohort

A single-stage design will be utilized to estimate overall survival, with a hypothesized rate of T-cell pathway induction of 64%= $H_1$  and 33%= $H_0$ . We will enroll 16 patients; this design has a two-sided Type I error of 0.05 and a power of 80%.

CONFIDENTIAL

This material is the property of the NYU School of Medicine. Do not disclose or use except as authorized in writing by the study sponsor

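### Neither cohort has the stated 80% power at a two-sided 5% level: exact power is about 65% with 24 patients and 66% with 16, and the sizes fit a one-sided 5% test

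*Combined protocol and SAP*

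**What the plan says.** Section 7.1 sets the main cohort's hypotheses: "a 12 month (1yr-OS) of 35% will be considered non-promising" and "an increase in the 1yr-OS to 60% will be considered promising". Section 7.2.2 then gives the design: "We will enroll 24 patients; this design has a two-sided Type I error of 0.05 and a power of 80" per cent. The synopsis (Sample Size) repeats the size and power without saying whether the test is one- or two-sided: "This will provide 80% power to detect an increase in the 1-year OS from 35% to 60%, using a 0.05-level test".

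For the surgical cohort, section 7.1 says "a T-cell pathway induction rate of 33% will be considered non-promising" and takes 64% as the promising rate. Section 7.2.3 says "We will enroll 16 patients; this design has a two-sided Type I error of 0.05 and a power of 80" per cent. The synopsis states the same design as "This will provide 80% power to detect an increase in the 1-year OS from 33% to 64%, using a 0.05-level test".

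No section names a hypothesis test or gives the number of successes that would count as positive. The only method stated for the main cohort's 1-year OS rate is an exact 95% confidence interval, of which the synopsis (Endpoints) says "with 24 patients, a 95% CI will be no more than 0.4 units wide for the main study cohort"; section 7.2.2 makes the same claim about its width.

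**The concern.** Twenty-four patients looks small for 80% power at a two-sided 5% level with 35% against 60%, and so does 16 for 33% against 64%. Both sizes are close to what a one-sided 5% test needs.

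If the two-sided level is meant, a regimen that truly reaches 60% at 1 year is missed about 35% of the time, not 20%. If the power is meant, the two-sided 5% statement is false. The two readings differ by one patient in the success count. With no count in the plan, that choice could be made after the data are seen.

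**Working it through.** **Inputs (all from the plan).** Main cohort: n = 24, p0 = 0.35, p1 = 0.60 (sections 7.1 and 7.2.2). Surgical cohort: n = 16, p0 = 0.33, p1 = 0.64 (sections 7.1 and 7.2.3). Two-sided alpha 0.05, claimed power 80%. No dropout allowance is stated, so n is used in full.

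**Method.** With X ~ Binomial(n, p), the exact upper tail at cut-off r is P(X ≥ r | p0) and the power is P(X ≥ r | p1). Two-sided 5% requires an upper tail of at most 0.025; one-sided 5% requires at most 0.05.

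| Cohort | Cut-off | Upper tail at p0 | Power at p1 | Meets two-sided 5%? | Meets one-sided 5%? |
|---|---|---|---|---|---|
| Main | ≥13/24 | 0.0423 | 78.7% | no | yes |
| Main | ≥14/24 | 0.0164 | 65.0% | yes | yes |
| Surgical | ≥9/16 | 0.0470 | 81.9% | no | yes |
| Surgical | ≥10/16 | 0.0148 | 65.7% | yes | yes |

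**Trying to reproduce 80%.** At the stated two-sided level the exact test gives 65.0% and 65.7%. The two-sided exact test that orders outcomes by likelihood has the same upper cut-offs and the same power. Large-sample formulas also fall short: the normal (score) formula gives 72.3% and 74.6%, and the arcsine formula 69.8% and 71.3%. Using the source fractions 5/15 and 9/14 in place of 33% and 64% gives 66.6% for the surgical cohort.

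**Sample size formula.** n = [z_α √(p0(1−p0)) + z_β √(p1(1−p1))]² / (p1−p0)², with z_β = 0.842.
- Main, two-sided (z_α = 1.960): [1.960 × 0.477 + 0.842 × 0.490]² / 0.25² = 29.0. One-sided (z_α = 1.645): 22.9.
- Surgical, two-sided: [1.960 × 0.470 + 0.842 × 0.480]² / 0.31² = 18.3. One-sided: 14.4.

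The planned 24 and 16 lie just above the one-sided values and below the two-sided ones. With an exact two-sided 5% test, the smallest sizes reaching 80% are 34 (≥18/34, power 84.5%) and 21 (≥12/21, power 81.2%).

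**Agreement with the planned interval.** The exact 95% CI is 0.328 to 0.744 at 13/24, which includes 35%, and 0.366 to 0.779 at 14/24, which excludes it. Read through its own planned interval, the main cohort therefore has the 65% cut-off.

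**The count on which it turns.** If true 1-year OS is 60%, P(X = 13) = 0.787 − 0.650 = 0.137. There is about a 14% chance of landing on the one count where the two readings disagree.

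**Interval width.** For n = 24 the exact 95% CI is widest at 12/24: 0.291 to 0.709, a width of 0.418. The width exceeds 0.4 for every count from 9 to 15. The number of survivors expected at 60% is 24 × 0.60 = 14.4, inside that range.

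**The case against.** The best defence is that the plan names no test, so an approximate two-sided test may have been meant. A two-sided score z-test with critical value 1.96 does reject at 13/24 (z = 1.969) and 9/16 (z = 1.978), with power 78.7% and 81.9%. The authors may therefore have used a nominal two-sided test rather than mislabelled a one-sided one. But that test's actual two-sided size is 0.0423 + 0.0133 = 0.0555 for the main cohort, where it also rejects at 3 or fewer survivors, and 0.0470 + 0.0146 = 0.0616 for the surgical cohort, where it also rejects at 1 or fewer. It recovers the power by exceeding the stated error rate. It would also call 13/24 positive while the planned exact interval includes 35%.

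Three further points deserve weight:
- The one-sided match is not perfect for the main cohort. Exact power is 78.7%, and the smallest size reaching 80% at one-sided 5% is 26.
- Sections 2.2 and 3.2 give the surgical cohort's primary aim as safety, feasibility and tolerability, so its power statement carries less weight than the main cohort's. It is still the only hypothesis used to size that cohort, and the synopsis lists the induction rate within the primary objective.
- The interval width and the synopsis slip are small. A width of 0.418 rounds to 0.4, and the synopsis names the right endpoint in the sentence before the wrong one. Neither would matter much alone.

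**Conclusion.** The concern holds. With two-sided 5% error controlled exactly, power is 65.0% for the main cohort and 65.7% for the surgical cohort, against 80% stated for each. None of the tests examined delivers both stated figures. The exact test is an inference, because the plan names none, but it is the natural one given the planned exact interval, and the usual two-sided approximate formulas also stay below 80%. How the authors arrived at 24 and 16 cannot be settled from the document; what can be said is that the sizes fit a one-sided 5% test, closely for 16 and within about 1.3 points of power for 24.

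This must be fixed because it concerns the error rate and power of the main cohort's primary endpoint, and because the conclusion at 13 of 24 is left undefined. The width claim and the synopsis endpoint are also wrong as written and can be corrected at the same time.

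**What to change.** Keep both sample sizes and put one true statement in sections 7.2.2 and 7.2.3 and in the synopsis. Name the test, its sidedness and the critical count.

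- **Option (a), one-sided 5%.** Promising if at least 13/24 (exact alpha 4.2%, power 79%) and at least 9/16 (alpha 4.7%, power 82%). Report a one-sided 95% lower bound or a 90% CI so that interval and decision agree; the exact 90% lower limits are 0.358 at 13/24 and 0.333 at 9/16 (0.3334 before rounding), above 35% and 33% respectively.
- **Option (b), two-sided 5%.** Promising if at least 14/24 (power 65%) and at least 10/16 (power 66%), with the planned 95% CI unchanged.

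The choice belongs to the sponsor, but it should be made before the outcomes are known. Also change the width claim in section 7.2.2 and the synopsis to no more than 0.42, and in the synopsis attribute the 33% to 64% comparison to the T-cell pathway induction rate.

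The cost is protocol wording and slightly less favourable stated figures. No extra patients or procedures are needed.

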### 1.1 Background

#### 1.1.1 Study Disease

About 15,000 new glioblastomas (GBM, WHO grade IV) are diagnosed each year in the US, and nearly all are fatal. Even with the relatively recent US FDA approvals of therapies for the treatment of either newly diagnosed (temozolomide in 2005) or recurrent (bevacizumab in 2009) GBM, the prognosis of GBM has not significantly changed in over 50 years. In recent multi-institutional randomized trials of newly diagnosed GBM, median survival times have been 15-16 months. Standard therapy for newly diagnosed GBM, which consists of 6 weeks of fractionated radiation to 60 Gy with concurrent and adjuvant temozolomide, results in a modest improvement in survival of patients with *MGMT* promoter methylated GBM tumors. However, patients with unmethylated *MGMT* GBM, which constitutes approximately half of all GBM, derive little, if any, benefit from temozolomide. Patients with *MGMT* unmethylated GBM have a particularly dismal median survival of 12 months and only 6% survive 2 years. Therefore, novel treatment paradigms are desperately needed for this particularly poor prognosis molecular subset of GBM patients.

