#### **6.8.3 Extended Follow-up Post-Treatment:**

Following the 90-day post-drug visit, all subjects will be contacted every 3 months ( $\pm 14$  days) to assess for study-treatment related toxicities, initiation of any new anti-cancer treatments, and survival status. Contact may be performed by a site visit, telephone contact, e-mail, or mail. The date of death, initiation of any new anti-cancer treatments and date of last contact should be documented if this information is available. All subjects will be followed post-treatment until death, withdrawal of permission to record at least survival data, or subject is lost to follow-up.

If a subject withdraws permission to record at least survival data after coming off treatment, this must be documented along with the date the subject withdraws permission as per details in Section 6.12.

Subjects will be considered lost to follow up if no medical records are available to be reviewed and two phone calls each to the subject and then the subject's next-of-kin (if the subject does not respond) are not returned over two consecutive 3 month periods.

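### The primary endpoint is scored at 48 weeks but tested against a 12-month null of 35%, which raises the false-positive rate and overstates 1-year and 2-year survival

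*Combined protocol and SAP*

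**What the plan says.** Section 7.2.2 (Main Study Cohort) sets the clock for the survival endpoints: "For endpoint analyses, one year will be defined as 48 weeks (8 cycles) and two years will be defined as 96 weeks (16 cycles"). These are whole numbers of 42-day cycles, and 96 weeks is also how section 5.2.1 defines the two-year treatment period.

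The benchmark is on a calendar clock. In section 7.1, "Based on these historical measures, a 12 month (1yr-OS) of 35% will be considered non-promising", and "an increase in the 1yr-OS to 60% will be considered promising". The synopsis repeats the pair. Section 7.1 builds them from historical proportions alive at 1 and 2 years: 50% and 6% for *MGMT*-unmethylated patients aged 70 or under with good function, and 21% to 32% at 1 year for elderly or poor-prognosis patients. Section 1.1.1 cites the same history: a "particularly dismal median survival of 12 months and only 6% survive 2 years".

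Section 7.2.2 gives 24 patients, a two-sided type I error of 0.05 and 80% power, with 1-year OS reported as a proportion with an exact 95% confidence interval. OS runs from treatment initiation. No section restates 35% or 60% at 48 weeks, explains the shorter year, or commits to a calendar-year analysis.

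**The concern.** The observed proportion and the null it is judged against refer to different times. Day 336 is 29 days short of a year, so a regimen with exactly the null 12-month survival has a higher proportion alive when the endpoint is read. With no concurrent control, the historical rate is the only comparator, and a shift in its time point goes straight into the type I error.

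The label is affected as well. A figure reported as 1-year OS would be 48-week OS, and readers would set it beside true 1-year rates. The same binary outcome feeds the biomarker analyses in section 7.2.4. Two-year OS, read 58 days early, has the same labelling problem.

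**Working it through.** **Inputs.** N = 24, p0 = 0.35 and p1 = 0.60 at 12 months (sections 7.1 and 7.2.2); endpoint read at 336 and 672 days (7.2.2). A year is taken as 365.25 days. The plan gives no success cutoff and no survival curve, so the cutoffs below are derived and the hazard shape is an assumption with a range.

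**Step 1: reproduce the design.** Exact binomial, X ~ Bin(24, p):

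| Rule | P(reject), p = 0.35 | Power, p = 0.60 |
|---|---|---|
| X ≥ 13 | 0.042 | 0.787 |
| X ≥ 14 | 0.016 | 0.650 |

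The first rule is a one-sided 5% test and comes close to the stated 80% power. The second fits the stated two-sided 5% test: 14 is the smallest count whose exact 95% interval (36.6% to 77.9%) lies above 35%. Both are carried forward, because the text says two-sided while the sample size fits one-sided.

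**Step 2: move the null to 48 weeks.** For a Weibull curve with shape k,

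S(336 d) = S(12 mo)^[(336/365.25)^k], with 336/365.25 = 0.920.

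For k = 1 (constant hazard): 0.35^0.920 = 0.381 and 0.60^0.920 = 0.625.

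**Step 3: false-positive rate when true 12-month OS is exactly 35%.**

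| Shape k | 48-week survival | X ≥ 13 | X ≥ 14 |
|---|---|---|---|
| Endpoint at 12 months | 35.0% | 4.2% | 1.6% |
| 0.7 (falling hazard) | 37.2% | 6.7% | 2.8% |
| 1 (constant) | 38.1% | 8.0% | 3.5% |
| 1.5 | 39.6% | 10.7% | 4.9% |
| 2 | 41.1% | 13.8% | 6.7% |

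Every 48-week row exceeds its limit: 5% for X ≥ 13, and 2.5% (the upper tail of a two-sided 5% test) for X ≥ 14. With a 52-week year and constant hazard the null is 37.9% and X ≥ 13 gives 7.8%, so the choice of year length hardly matters.

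**Step 4: which shape do the plan's own figures suggest?** A Weibull curve through 50% at 1 year and 6% at 2 years has k = ln[ln(0.06)/ln(0.50)] / ln 2 = ln(4.06)/ln 2 ≈ 2.0. Those were fitter patients aged 70 or under, so this is indicative only, but it puts constant hazard at the mild end.

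**Step 5: size of the overstatement.** A true 1-year OS of 60% reads as 61.8% (k = 0.7) to 64.9% (k = 2). For two years, 672/730.5 = 0.920, so a true 6% reads as 0.06^0.920 = 7.5% under constant hazard, and 7.0% to 9.2% across k = 0.7 to 2.

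**The case against.** The direction cannot be disputed; the size can.

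- **The cutoffs are not in the plan.** The synopsis words the objective as estimation, and section 7.2.2 specifies an interval, not a success rule. This stands: the error rates are conditional on derived cutoffs.
- **Under the stated two-sided test the overall size may still hold.** Rejection at X ≥ 14 or X ≤ 3 has total probability 0.016 + 0.013 = 0.030 at 35%, and 0.035 + 0.006 = 0.041 at 38.1%, still below 0.05. It passes 0.05 (0.053) only at shape 1.5. This is correct, but only the upper tail supports an efficacy claim, and that tail goes from 1.6% to 3.5% against 2.5%.
- **The null is a rounded judgement.** It was chosen from historical rates running from 21% to 50%, and a shift of 3 points is small beside that and beside an interval about 0.4 wide. Under constant hazard at the null it is 24 × (0.381 − 0.350) ≈ 0.7 patients. This is fair on precision. But the imprecision of the 35% could fall either way, whereas the 48-week reading always favours the regimen.
- **The definition is prespecified beside H0 and H1, so the hypothesised rates could be read as 48-week rates.** Section 7.1 attaches 12 months to the 35% in so many words, which rules that reading out unless the text is changed. Prespecification does not align the endpoint with the null.
- **Calendar 12-month survival could be read off the Kaplan-Meier curve.** It could, and median OS is unaffected, but the plan does not commit to reporting it, and it is not the primary analysis.

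**Conclusion.** The concern holds. Reading the endpoint at 48 weeks against a 12-month null can only raise the false-positive rate, and does so whenever deaths occur in the omitted 29 days; that needs no model. The size depends on assumptions. Under constant hazard the chance of a false efficacy signal about doubles, to 8.0% (X ≥ 13) or 3.5% in the upper tail (X ≥ 14). Over Weibull shapes 0.7 to 2 the ranges are 6.7% to 13.8% and 2.8% to 6.7%. With constant hazard, the total size of a two-sided exact test stays under 5%. For two-year OS, which has no hypothesis test, the consequence is overstatement and a misleading label. Because this concerns the primary comparison, it should be corrected before the analysis.

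**What to change.** In section 7.2.2, define 1-year OS as alive at 365 days (12 months) and 2-year OS as alive at 730 days (24 months) from first dose. Keep 48 and 96 weeks only as treatment-duration terms, and use the 365-day status for the binary outcome in section 7.2.4. H0, H1 and N stay as written, and the error rates return to 4.2% or 1.6%.

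If 48 weeks must stay, the alternative is to restate both hypotheses at 48 weeks with a justified conversion and a stated cutoff. Under constant hazard that is about 38.1% against 62.5%. X ≥ 13 would then have an error of 8.0%, so a one-sided 5% test would need X ≥ 14 (error 3.5%, power 74.0%). This is the weaker choice, because it rests on a hazard shape that the plan does not supply and the result still could not be set beside 1-year figures.

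The cost of the preferred change is one sentence. Section 6.8.3 already provides that "All subjects will be followed post-treatment until death, withdrawal of permission to record at least survival data, or subject is lost to follow-up", so no visits or data are added. The last patient's readout comes 29 days later, and the estimate will be slightly less favourable.
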